## **2.3 Efficacy and Safety Variables**

### **2.3.1 Efficacy Variables**

Efficacy variables in this trial will be captured via the IVRS on a daily basis (CSBM frequency, SBM frequency, consistency, straining, and abdominal symptoms of pain, discomfort, bloating, fullness, and cramping) or weekly basis (IBS severity, and constipation severity) during the screening (baseline) period and the 26 week treatment period. Adequate relief of IBS symptoms and degree of relief of IBS symptoms will be collected weekly during the treatment period. The IBS-QOL will be collected at the randomization visit, the week 12 visit, and the week 26 visit. Treatment satisfaction will be recorded at the end of each month during the treatment period through week 20 and again at week 26 Use of rescue medication is also collected daily throughout the screening and treatment periods. Rescue medication usage is incorporated into the derivation of the efficacy variables but is not in itself considered an efficacy variable.

The primary efficacy variable will be the overall responder rate. An overall responder will be defined as a weekly responder for the first 6/12 weeks where both CSBM and abdominal pain response criteria were met for the week. The CSBM and abdominal pain response criteria are defined below. The weekly overall responder rates will be summarized for each week of the treatment period. An endpoint week will be defined as the last valid week during the treatment period with an overall responder criteria assessment.

The CSBM response criteria are defined as an increase of one or more change in average weekly CSBMs from baseline. The definition of a CSBM is as follows: A CSBM is a SBM for which the subject responds “yes” to the following question; “Did you feel like you completely emptied your bowels?” Any SBM which is preceded within 24 hours by the use of rescue medication will not be counted as a SBM and therefore also not counted as a CSBM as defined above. Should a subject not have data reported for a given week (either due to a gap in reporting or due to discontinuation), the subject will be considered to be a non-responder for the week.

A key secondary efficacy variable will be the overall CSBM responder rate. An overall CSBM responder will be defined as a weekly CSBM responder for the first 6/12 weeks where the CSBM response criteria were met for the week. The weekly CSBM responder rates will be summarized for each week of the treatment period. An endpoint week will be defined as the last valid week during the treatment period with a CSBM response criteria assessment.

The average weekly CSBMs will be calculated as the sum of the number of CSBMs reported during each day of the defined weekly period divided by the number of days CSBMs were reported multiplied by 7. A valid week will require at least 4 days of SBM reporting. The average weekly CSBMs and change from baseline (where baseline is the average of the 2-weeks during the screening period) for each week of the treatment period will be summarized. An endpoint week will be defined as the last valid week during the treatment period with an average weekly CSBM.

The abdominal pain response criterion is defined as a decrease of 30% or more of percent change in average weekly worst abdominal pain from baseline. Abdominal pain will be scored daily using the scale 0 = No pain to 10 = very severe pain. The average weekly abdominal pain score will be calculated as the average score for all days during a valid week. A valid week will require at least 4 days of abdominal pain reporting. Should a subject not have data reported for a given week (either due to a gap in reporting or due to discontinuation), the subject will be considered to be a non-responder for the week.

The average weekly abdominal pain score and percent change from baseline (where baseline is the average of the 2-weeks during the screening period) for each week of the treatment period will be summarized. An endpoint week will be defined as the last valid week during the treatment period with an average weekly abdominal pain score.

A key secondary efficacy variable will be the overall abdominal pain responder rate. An overall abdominal pain responder will be defined as a weekly abdominal pain responder for the first 6/12 weeks where the abdominal pain response criteria were met for the week.

Additional key secondary efficacy variables consist of the overall responder rate, overall CSBM responder rate, and overall abdominal pain responder rate calculated using a 13/26 week response criteria. These responder rates encompass the entire 26-week treatment period. Hence, for 13 out of the 26 weeks during the treatment period, the subject met the responder criteria for the 6/12 week responder rates.

Additional key secondary efficacy variables consist of the overall responder rate, overall CSBM responder rate, and overall abdominal pain responder rate calculated using a 9/12 week response criteria. Hence, for 9 out of the first 12 weeks during the treatment period, the subject met the responder criteria for the 6/12 week responder rates. In addition, for the first 9/12 week CSBM responder criteria, it is also required that the average weekly CSBMs for the week are  $\geq 3$ .

For each of the efficacy variables described above (i.e., first 6/12, 13/26, and first 9/12 responders for respective weeks), several sensitivity analyses will be done. Instead of assuming non-response for missing weeks or weeks with less than 4 days of valid diary data, a sensitivity analysis will be carried out imputing response for these weeks. Similarly, instead of assuming a 30% reduction for percent change in abdominal pain, these analyses will be repeated using a 40% reduction and a 50% reduction as response criteria. Note that for these last 2 analyses, the CSBM responder analyses will not be repeated, only the overall and abdominal pain responder rates.

Secondary efficacy variables will include the following:

The durable overall responder rate, durable overall CSBM responder rate, and durable overall abdominal pain responder rate will be secondary efficacy variables. The durable responder rates use the same first 9/12 week response criteria and in addition, require the last 3/4 weeks of the first 12 weeks of the treatment period to meet the response criteria.

The proportion of subjects with  $\geq 3$  CSBMs per week will be summarized for the baseline and treatment periods. An endpoint week will be defined as the last valid week during the treatment period with an average weekly CSBM.

Average weekly SBMs will be calculated as described above for average weekly CSBMs. Change from baseline for each week of the 26-week treatment period will be summarized using the observed data. An endpoint week will be defined as the last valid week during the treatment period with an average weekly SBM.

Subjects will record the consistency of each of their bowel movements on a daily basis through the IVRS utilizing the BSFS scale (Appendix B of the protocol). The average weekly stool consistency will be calculated as the average score for all valid SBMs during the week. For purposes of calculating an average, days with no stools will be scored a 0. Change from baseline for each week of the 26-week treatment period will be summarized using the observed data. Baseline will be calculated as described for the CSBMs and SBMs. An endpoint week will be defined as the last valid week during the treatment period with an average weekly stool consistency.

Straining will be scored for each SBM using the scale 1 = not at all, 2 = a little bit, 3 = a moderate amount, 4 = a great deal, 5 = an extreme amount. The average weekly straining score will be calculated as the average score for all valid SBMs during the week. Change from baseline for each week of the 26-week treatment period will be summarized using the observed data. Baseline will be calculated as described for the CSBMs and SBMs. An endpoint week will be defined as the last valid week during the treatment period with an average weekly straining score.

Abdominal discomfort, abdominal bloating, abdominal fullness, and abdominal cramping will be scored daily using the 0-10 point scale with 0 representing no presence of the symptom and 10 representing very severe presence of the symptom. The average weekly scores will be calculated as the average score for all days during a valid week. Percent change from baseline for each week of the 26-week treatment period will be summarized. In addition, responders at each week (i.e., 30% improvement from baseline) and for the first 6/12 weeks, 9/12 weeks, and 13/26 weeks on treatment will be defined in a similar manner as for abdominal pain responder rates. If no data is present to constitute a valid week, it will be assumed the subject did not respond. Otherwise, observed data will be used to summarize the average weekly abdominal symptom. Baseline will be calculated as described for the CSBMs and SBMs. An endpoint week will be defined as the last valid week during the treatment period with an average weekly abdominal symptom score. Each symptom will be assessed separately so it is possible for different symptoms to have different endpoint weeks.

IBS severity and constipation severity will be scored on a weekly basis using the scale 1 = None, 2 = Mild, 3 = Moderate, 4 = Severe, 5 = Very Severe. IBS severity scores and constipation severity scores for each week of the study will be summarized as categorical and continuous data. Observed data will be used for the summaries. Baseline for these severity ratings will be the average of the two ratings during the screening period. An endpoint week will be defined as the last valid week during the treatment period with an IBS severity or constipation severity rating.

Adequate relief of IBS symptoms (1 = yes, and 2 = no) will be asked on a weekly basis during the treatment period. The percentage of subjects with adequate relief for each week of the study will be summarized using observed data. An endpoint week will be defined as the

last valid week during the treatment period with an adequate relief of IBS symptoms response.

Degree of relief of IBS symptoms will be scored on a weekly basis during the treatment period using 1=completely relieved, 2=considerably relieved, 3=somewhat relieved, 4=unchanged, 5=somewhat worse, 6=considerably worse, 7=as worse as I can imagine. Degree of relief scores for each week of the study will be summarized as categorical and continuous data using observed data. An endpoint week will be defined as the last valid week during the treatment period with a degree of relief of IBS symptoms response.

The IBS-QoL is a validated quality of life tool used for IBS patients (see Appendix D of the protocol). Subjects will be asked to complete this assessment a Visit 2 (randomization visit), Visit 6 (at 12-weeks of treatment), and Visit 9 (at the end of the 26-week treatment period). The IBS-QoL includes 34 individual questions which measure 8 subscales found to be relevant to patients with IBS: dysphoria, interference with activity, body image, health worry, food avoidance, social reaction, sexual, relationships and overall. Each of the subscale scores is calculated using the criteria described in the IBS-QoL user manual attached as [Appendix 1](#) to this SAP.

All items in the IBS-QoL are negatively framed with the greatest response scale equaling the worst quality of life. When scored, all items are reversed so that the as IBS-QoL scores increase, quality of life increases. i.e., 1 changes to 5, 2 changes to 4, 3 stays as 3, 4 changes to 2, and 5 changes to 1. Then the reversed individual responses to the 34 items are summed and averaged for a total score and then transformed to a 0-100 scale for ease of interpretation with higher scores indicating better IBS specific quality of life using the following formula:

$$\text{Subscale Score} = \frac{(\text{the sum of the items} - \text{lowest possible score})}{\text{possible raw score range}} \times 100.$$

Actual values and change from baseline values for each of the subscale scores will be calculated and summarized.

Treatment satisfaction will be recorded by the subject at the end of each month during the treatment period (Visits 4, 5, 6, 7, and 8), and at the end of the treatment period (Visit 9). Using the scale: 1= not at all satisfied, 2= a little satisfied, 3= moderately satisfied, 4 =quite satisfied, 5= very satisfied. The treatment satisfaction score will be summarized as a categorical and continuous variable.

The following summarizes the efficacy variables planned for this study:

Table 2-1 Summary of Efficacy Variables and Designation	
Variable Designation	Variable name
Primary	6/12 week overall responder rate
Key Secondary	6/12 week overall CSBM responder rate
Key Secondary	6/12 week overall abdominal pain responder rate

Key Secondary	9/12 week overall responder rate
Key Secondary	9/12 week overall CSBM responder rate
Key Secondary	9/12 week overall abdominal pain responder rate
Key Secondary	13/26 week overall responder rate
Key Secondary	13/26 week overall CSBM responder rate
Key Secondary	13/26 week overall abdominal pain responder rate
Sensitivity	6/12 week overall responder rate with imputed responders
Sensitivity	6/12 week overall CSBM responder rate with imputed responders
Sensitivity	6/12 week overall abdominal pain responder rate with imputed responders
Sensitivity	13/26 week overall responder rate with imputed responders
Sensitivity	13/26 week overall CSBM responder rate with imputed responders
Sensitivity	13/26 week overall abdominal pain responder rate with imputed responders
Sensitivity	9/12 week overall responder rate with imputed responders
Sensitivity	9/12 week overall CSBM responder rate with imputed responders
Sensitivity	9/12 week overall abdominal pain responder rate with imputed responders
Sensitivity	6/12 week overall responder rate with 40% change in abdominal pain
Sensitivity	6/12 week overall 40% change in abdominal pain responder rate
Sensitivity	13/26 week overall responder rate with 40% change in abdominal pain
Sensitivity	13/26 week overall 40% change in abdominal pain responder rate
Sensitivity	9/12 week overall responder rate with 40% change in abdominal pain
Sensitivity	9/12 week overall 40% change in abdominal pain responder rate
Sensitivity	6/12 week overall responder rate with 50% change in abdominal pain
Sensitivity	6/12 week overall 50% change in abdominal pain responder rate
Sensitivity	13/26 week overall responder rate with 50% change in abdominal pain
Sensitivity	13/26 week overall 50% change in abdominal pain responder rate
Sensitivity	9/12 week overall responder rate with 50% change in abdominal pain
Sensitivity	9/12 week overall 50% change in abdominal pain responder rate
Secondary	Durable overall responder rate
Secondary	Durable overall CSBM responder rate
Secondary	Durable overall abdominal pain responder rate
Secondary	Weekly overall responder rate
Secondary	Weekly CSBM responder rate
Secondary	Weekly abdominal pain responder rate

Secondary	Weekly proportion of subjects with $\geq 3$ CSBMs per week
Secondary	Average weekly CSBMs
Secondary	Average weekly SBMs
Secondary	Average weekly stool consistency
Secondary	Average weekly straining score
Secondary	6/12, 9/12, and 13/26 Overall abdominal discomfort responder rate
Secondary	6/12, 9/12, and 13/26 Overall abdominal bloating responder rate
Secondary	6/12, 9/12, and 13/26 Overall abdominal cramping responder rate
Secondary	6/12, 9/12, and 13/26 Overall abdominal fullness responder rate
Secondary	Weekly abdominal discomfort responder rate
Secondary	Weekly abdominal bloating responder rate
Secondary	Weekly abdominal cramping responder rate
Secondary	Weekly abdominal fullness responder rate
Secondary	Average weekly abdominal pain score
Secondary	Average weekly abdominal discomfort score
Secondary	Average weekly abdominal bloating score
Secondary	Average weekly abdominal cramping score
Secondary	Average weekly abdominal fullness score
Secondary	Weekly IBS severity score
Secondary	Weekly constipation severity score
Secondary	Weekly adequate relief of IBS symptoms
Secondary	Weekly degree of relief of IBS symptoms score
Secondary	IBS-QOL (9 subscales)
Secondary	Treatment satisfaction

### 2.3.2 Safety Variables

Safety variables will include adverse event (AE) reporting throughout the trial, clinical laboratory tests (serum chemistry, hematology, and urinalysis), vital signs (including body weight and body mass index [BMI]), 12-lead ECG, and physical examinations.

## 3. STATISTICAL METHODOLOGY

### 3.1 Determination of Sample Size

A sample size of 300 in each treatment group would achieve 95% power to detect a difference of 0.15 (15%) between the placebo and tenapanor 50 mg BID first 6/12 week

overall responder rate when the tenapanor 50 mg BID responder rate is at least 45% under the alternative hypothesis and the responder rate in the placebo group is no closer than 15% from tenapanor 50 mg BID. The test statistic used was the two-sided Fisher's exact test with significance level of 0.050 (5%). This sample size also has 80% power to detect an 11.6% difference in responder rates between the treatment groups when the responder rates are in the same range as above.

### **3.2 Analysis Sets**

#### Safety Analysis Set:

All subjects who receive at least one dose of study drug will be included in all analyses of safety data. Such subjects will be analyzed according to the treatment actually received.

#### Intent to Treat (ITT) Analysis Set:

All subjects who meet the study entry inclusion/exclusion criteria, are randomized and receive at least one dose of study drug will be included in the ITT analysis set. Subjects will be analyzed according to the treatment group into which they were randomized. The ITT analysis set will be the primary analysis set for efficacy analysis.

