At the end of the screening period, prior to the subject returning for Visit 2 (Randomization), a member of the site staff will confirm a subject's eligibility with regard to the information they have reported in their electronic diary during screening. If the information captured in the diary deems them eligible, and they continue to meet the inclusion criteria at Visit 2, a member of the site staff will randomize the subject into a treatment group using an interactive web-response system (IWRS).

Subjects will be randomized into a treatment group according to a computer-generated central randomization schema. All subjects who receive at least one dose of study drug, with at least one valid week of efficacy assessment data will be included in the intention-to-treat (ITT) analysis set. All subjects who receive at least one dose of study drug will be included in all analyses of safety data.

During the 26-week double-blind treatment period, subjects will continue to record daily and weekly assessments via a touch-tone telephone diary system as instructed. Subjects will be seen weeks 2, 4, 8, 12, 16, 20, and 26 (Days 15, 29, 57, 85, 113, 141, and 183) during the treatment period. Subject compliance with daily diary entries will be monitored on an ongoing basis by the clinical site staff. Subject compliance

with study drug will also be monitored closely by clinical site staff throughout the study

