10.3. Analysis Sets

Safety Analysis Set:

All subjects who receive at least one dose of study drug will be included in all analyses of safety data. Such subjects will be analyzed according to the treatment actually received.

Intent to Treat (ITT) Analysis Set:

All subjects who meet the study entry inclusion/exclusion criteria, receive at least one dose of study drug, and have at least one valid week of efficacy assessment data (minimum of 4 days) will be included in the ITT analysis set. Subjects will be analyzed according to the treatment group into which they were randomized. The ITT analysis set will be the primary analysis set for efficacy analysis.

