#### Per-Protocol (PP) Analysis Set

All subjects included in the ITT analysis set who complete the study as planned with no major protocol deviations will be included in the PP analysis set. Membership in this analysis set will be determined at a data review meeting prior to unblinding the randomization. This analysis set will be used as a sensitivity analysis relative to the ITT analysis set.

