### **3.6.1 Subject Disposition**

Subject disposition information will be summarized by treatment group and overall. The number and percent of subjects who are randomized, who took a dose of study drug, who complete the study, and who withdraw early from the study will be presented. The primary reason for early withdrawal will also be tabulated. The number of subjects randomized will be used as the denominator for the percentage calculation. Subject disposition, inclusion / exclusion criteria, and protocol deviations will be listed.

The number and percent of subjects in each analysis set will also be tabulated.

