### **3.7.1 Efficacy Analyses**

The primary objective of this study will be to demonstrate the superiority of tenapanor over placebo in the proportion of subjects who are weekly overall responders at 6 or more of the first 12 weeks of treatment.

The ITT analysis set will be used for the analysis of the primary, key secondary, secondary, and all sensitivity analyses. The PP analysis set will be used for the analysis of the primary, key secondary, and secondary variables as a separate sensitivity analysis. All efficacy analyses will be carried out based on observed cases (OC) with imputation as described previously in [Section 3.3](#).

All efficacy variables involving responder rates or proportions will be analyzed using a Cochran-Mantel-Haenszel (CMH) test with pooled investigator site as a stratification (adjustment) variable. These analyses include subject based variables and variables summarized weekly. Summary statistics will include the pairwise risk difference with placebo along with the asymptotic 95% confidence interval (CI). The adjusted relative risk (adjusted for pooled investigator site) will be based on the ratio of responder rates for tenapanor 50 mg BID versus placebo. The 95% CI versus placebo will also be presented for the adjusted relative risk.

All change from baseline or percent change from baseline continuous efficacy variables derived from the daily IVRS questions (i.e., average weekly CSBMs, SBMs, stool consistency, straining score, abdominal symptoms of pain, discomfort, bloating, fullness, and cramping), as well as the weekly IBS severity, constipation severity, and IBS QOL will be analyzed using an analysis of covariance (ANCOVA) model with terms for pooled investigator site, treatment, and baseline as the covariate. These analyses include variables summarized weekly or on a visit basis.

Actual values for degree of relief of IBS symptoms and treatment satisfaction will be analyzed using an analysis of variance (ANOVA) model with terms for pooled investigator site and treatment.

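### The primary ITT set drops randomised, dosed subjects later found to have failed an entry criterion; no efficacy analysis includes them, and no blinded decision on their removal is required

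*SAP*

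**What the plan says.** SAP 3.2 limits the ITT set to "All subjects who meet the study entry inclusion/exclusion criteria, are randomized and receive at least one dose of study drug" and names it the primary set for efficacy. Protocol 10.3 and the Protocol Summary (Statistical Considerations) carry the same eligibility clause: "All subjects who meet the study entry inclusion/exclusion criteria, receive at least one dose of study drug, and have at least one valid week". The SAP drops their valid-week condition but keeps eligibility. Protocol Section 4 has no eligibility clause: "All subjects who receive at least one dose of study drug, with at least one valid week of efficacy assessment data will be included".

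SAP 3.7.1 states: "The ITT analysis set will be used for the analysis of the primary, key secondary, secondary, and all sensitivity analyses". The only other efficacy set is per-protocol, defined in SAP 3.2 as "All subjects included in the ITT analysis set who complete the study as planned with no major protocol deviations". For that set the SAP adds: "Membership in this analysis set will be determined at a data review meeting prior to unblinding the randomization". There is no matching sentence for ITT.

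On reporting, SAP 3.6.1 says "The number and percent of subjects in each analysis set will also be tabulated" and "Subject disposition, inclusion / exclusion criteria, and protocol deviations will be listed".

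**The concern.** A set called ITT would normally keep everyone randomised, or everyone randomised and dosed. Here membership depends on a judgement that can be made after randomisation. Entry criteria are scheduled only at Visits 1 and 2 and confirmed before randomisation (protocol 7, 8.2 and 8.2.1). The clause therefore matters for facts that were already true at entry but found later, for example when case report forms are checked against source documents during monitoring (protocol 8.5). By then the subject may have weeks of diary outcomes.

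Removal biases the comparison only if it is both unequal between arms and linked to outcome. Deciding blind is the usual guard against that, and the plan does not require it for the primary set. Nor would any planned efficacy analysis show what the removals did. The stake is the primary test, which also opens the sequence of eight key secondary tests in SAP 3.7.1.

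**Working it through.** **1. Where does a late-found entry violator appear?**

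| Set | Condition | Violator included? |
|---|---|---|
| Safety (SAP 3.2) | dosed | yes, safety only |
| ITT (SAP 3.2) | meets entry criteria, randomised, dosed | no |
| Per-protocol (SAP 3.2) | in ITT, completed, no major deviation | no |

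The primary, key secondary, secondary and sensitivity analyses use ITT, and the per-protocol repeats use a subset of it. The violator is in none of them. Read literally, protocol Section 4 would include the same subject, given one valid week.

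**2. The plan's own figure.** SAP 3.1 assumes 300 per group, 45% on tenapanor, a 15-point difference (so 30% on placebo) and a two-sided Fisher's exact test at 0.05. Full enumeration gives 96.1% power against the stated 95%. For 45% vs 33.4% (the 11.6-point difference) it gives 80.8% against the stated 80%. Both reproduce, so 45% and 30% are used below.

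**3. Shift in the estimate at the planned rates.** Responders are 135/300 and 90/300. Remove *a* tenapanor and *b* placebo non-responders (assumed counts): difference = 135/(300 − a) − 90/(300 − b).

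| a, b | Calculation (%) | Difference (points) |
|---|---|---|
| 0, 0 | 45.00 − 30.00 | 15.0 |
| 3, 3 | 45.45 − 30.30 | 15.2 |
| 9, 9 | 46.39 − 30.93 | 15.5 |
| 15, 15 | 47.37 − 31.58 | 15.8 |
| 9, 3 | 46.39 − 30.30 | 16.1 |
| 3, 9 | 45.45 − 30.93 | 14.5 |

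**4. False-positive rate with no true effect.** Assume 30% responders in both arms and 300 per arm. Each subject is excluded with probability e, and excluded subjects respond at rate r. The rate among those retained is (0.30 − e·r)/(1 − e). The test is a single-stratum Cochran-Mantel-Haenszel test without continuity correction, |z| > 1.96, with probabilities from exact binomial summation. The planned stratification by pooled site is not modelled.

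| Excluded, tenapanor / placebo | r | Favouring tenapanor | Two-sided |
|---|---|---|---|
| 1% / 1% and 3% / 3% | 0 | 2.50% | 5.00% |
| 2% / 1% | 0 | 3.01% | 5.07% |
| 3% / 1% | 0 | 3.63% | 5.31% |
| 2% / 1% | 15% | 2.75% | 5.01% |
| 3% / 1% | 15% | 3.02% | 5.07% |
| 3% / 1% | 30% | 2.50% | 4.99% |

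Example, third row: 0.30/0.97 = 30.93% and 0.30/0.99 = 30.30%, a spurious gap of about 0.6 points. With the imbalance reversed (1% / 3%, all non-responders), the rate favouring tenapanor falls to 1.68%.

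**5. A borderline result (assumed counts).** With a pooled two-proportion z test, 112/300 vs 90/300 gives p = 0.057. Removing three tenapanor non-responders (112/297 vs 90/300) gives p = 0.047.

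**6. Cost in power of keeping violators.** The worst case is no drug effect in violators, so the tenapanor rate is 0.30 + 0.15(1 − v). Fisher power at v = 1%, 2%, 5% and 10% is 95.8%, 95.5%, 94.3% and 91.9%. Excluding them equally instead (297, 294, 285 or 270 per arm at 45% vs 30%) gives 96.0%, 95.9%, 95.4% and 94.1%.

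**The case against.** The strongest reply is that a blinded decision is already implied. Per-protocol members must first be in ITT, and per-protocol membership is fixed before unblinding, so the meeting has to consider ITT status. That holds for subjects placed in the per-protocol set. It fails for a subject kept out as a non-completer or major deviator, whose ITT status can stay open. Sign-off of the SAP before unblinding (protocol Section 10) fixes the definition, not each subject's membership. The separate programming document in SAP 4 cannot be seen and is not described as deciding membership.

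Second, the exposure is narrow. Diary criteria are checked electronically (protocol 5.4), eligibility is confirmed before randomisation, and facts true at entry should be balanced by randomisation. This stands, and it is why the effect is expected to be small. What remains is unequal detection or judgement after randomisation. Only the stable-dosage note in exclusion 6 (protocol 5.3) could reach behaviour on treatment, and only if a breach is read as failing entry rather than as a protocol deviation.

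Third, protocol Section 4 may be shorthand, since its narrative has already described eligible subjects. That is a fair reading, but the two texts still place a late-found violator differently.

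Fourth, the 3.6% figure is one-sided and needs a threefold imbalance with every excluded subject a non-responder. The planned two-sided test gives 5.3% in that case. This is correct, and the milder cases are shown for that reason.

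Fifth, set sizes are tabulated and entry criteria are listed. A reader can therefore see how many subjects were dropped, but not the effect on the result.

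**Conclusion.** The concern holds. The primary set allows a post-randomisation exclusion, no efficacy analysis retains the excluded subjects, and the plan does not require the decision to be made blind. It should be fixed, but it does not threaten the trial. With equal or outcome-neutral exclusions the error rate is unchanged. Under the unequal scenarios examined, the two-sided rate reaches at most 5.3%, and the estimated difference at the planned rates moves by about a point in either direction (16.1 or 14.5 against 15.0). All exclusion counts and response rates among excluded subjects are assumptions. The documents do not show how many violators there were, or whether exclusions were in practice decided blind.

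**What to change.** In SAP 3.2, define ITT as all randomised subjects who receive at least one dose, analysed as randomised. Weeks without valid data are scored as non-response, as SAP 3.3 already plans. Exclude entry violators only from the per-protocol set or a named sensitivity set, and fix the list at the existing pre-unblinding meeting. State that this definition governs over the Protocol Summary and protocol Sections 4 and 10.3.

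If the eligibility clause is kept, the minimum is to extend the pre-unblinding meeting to ITT exclusions and add a sensitivity analysis of the primary endpoint in all randomised, dosed subjects.

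The cost is wording, with no new data. Protocol Section 10 has the SAP confirm the analysis sets and lets it address changes to that section. It also says the primary analysis will not change, so the revision should be recorded openly before unblinding. SAP 1 rules out later deviation from the primary analyses, so this should be settled before sign-off. Editing the Protocol Summary or Section 4 would need written IRB/IEC approval (protocol 11.5), so a governing statement in the SAP is cheaper. The downside is that responder rates or the difference may look slightly less favourable. Even with no drug effect in violators, keeping them costs under 2 points of power against the full 96.1% if they are 5% or fewer.
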